15.0 Other Approvals

15.1 Describe any approvals that will be obtained prior to commencing the research (e.g., school, external site, funding agency, laboratory, radiation safety, or biosafety).

Response:

IRB approval for procedures taking place at Virginia Tech, DENT Neurologic Institute, and the Virginia Carilion Clinic.

N/A: This study does not require any other approvals.

16.0 Provisions to Protect the Privacy Interests of Subjects

16.1 *Describe how you will protect subjects' privacy interests during the course of this research.*

NOTE: Privacy refers to an individual's right to control access to him or herself. Privacy applies to the person. Confidentiality refers to how data collected about individuals for the research will be protected by the researcher from release. Confidentiality applies to the data.

Examples of appropriate responses include: "participant only meets with a study coordinator in a classroom setting where no one can overhear", or "the participant is reminded that they are free to refuse to answer any questions that they do not feel comfortable answering."

Response:

Prospective participants may contact the laboratory of their own free will and are thus controlling access to their privacy. All data will be collected in a secure laboratory environment in password protected databases in which only study staff has access. Participants will only interact with project research staff and sessions will take place in a private laboratory room that includes a closed circuit television monitoring system that will be monitored by the experimenter to ensure participant protocol adherence and safety. Participants are reminded that they are free to refuse to answer any questions that they do not feel comfortable answering and that all information is kept confidential to the extent provided by law.

16.2 *Indicate how the research team is permitted to access any sources of information about the subjects.*

*NOTE: Examples of appropriate responses include: school permission for review of records, consent of the subject, HIPAA waiver. This question **does apply** to records reviews.*

Response:

Participants will be recruited using a secure database of interested participants maintained by the Division of Behavioral Medicine and approved for use by previous IRB committees. Potential participants will be contacted if they had indicated that they are willing to be contacted for participation in studies and thus control their own participation. A HIPAA waiver has been completed for the recruitment of participants through medical records, which is completed through the physician's office with the consent of the primary care physician. The research team may also contact primary care physicians to confirm eligibility after participants have completed consent/HIPAA/medical release forms.

17.0 Data Management and Analysis

17.1 Describe the data analysis plan, including any statistical procedures. This section applies to both quantitative and qualitative analysis.

Response:

Analytic plan is to use factorial ANCOVA to compare between group differences in different measures of DD, executive function and fMRI-measured brain function for subjects randomly assigned to poverty/neutral conditions and EFT/ERT. Covariates will be used if significant differences between groups are observed in subject characteristics. We predict a main effect of neutral/poverty, such that those assigned to poverty will have higher DD than those assigned to neutral, and an interaction between poverty/neutral and EFT such that in the poverty condition, EFT will reduce the discounting to levels achieved by the wealth, ERT subjects. We also predict when participants who receive EFT under challenge of poverty that EFT will increase activation in brain regions associated with delay of gratification (LPFC and AC) and prospection (hippocampus) relative to those who receive EFT under similar challenges.

17.2 If applicable, provide a power analysis.

NOTE: This may not apply to certain types of studies, including chart/records reviews, survey studies, or observational studies. This question is asked to elicit whether the investigator has an adequate sample size to achieve the study objectives and justify a conclusion.

Response:

The sample size is based on our studies of EFT versus ERT on DD in overweight and obese subjects, which showed an average AUC of $0.54 + 0.28$, and our unpublished research that poverty simulations reduces DD by 34%. We estimate in the ERT condition, neutral simulations will lead to less discounting and higher AUC than poverty simulations (0.54 vs 0.36). We estimate in EFT conditions, that simulations of neutral are associated with a small improvement in discounting in comparison to poverty simulations (0.63 vs 0.54). These predictions suggest that DD in EFT/Poverty and ERT/Wealth will be equivalent. The effect size for this interaction is 0.35. Using the overall SD we observed of 0.28, alpha of .05 and power of 0.80, we can show the effect size for this interaction with 17 Ss/group, or 68 total, or 34 per site in the behavioral portion and in the imaging portion. To be conservative, we will study up to 100 subjects.

17.3 Describe any procedures that will be used for quality control of collected data.

Response:

The principal investigator will be responsible for ensuring data integrity and safety monitoring for human subjects who are involved in the research and communicating any negative outcomes of the data and safety monitoring plans (DSMP) reviews or any serious event or problem (SEP) that occur to the SBSIRB and other required offices/agencies. Materials will be checked to make sure that

all study data are coded with a unique participant ID. The ID will be linked only by a name through a master list kept by the project coordinator in a password-protected file.

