4.0 Study Design

4.1 *Describe and explain the study design (e.g. case-control, cross-sectional, ethnographic, experimental, interventional, longitudinal, observational).*

Response: This study is an experimental between-subjects design; subjects in the behavioral arm will be randomized to poverty/neutral scenarios crossed with EFT/ERT in a 2 x 2 factorial design. Subjects in the fMRI arm will be randomized to one of two groups: episodic future thinking (EFT) versus episodic recent thinking (ERT) control.

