fMRI Arm: If it is determined that the participant is willing and eligible to complete an fMRI they may be entered into the fMRI arm of this study. For these participants, the first visit is identical to that of the first visit in the behavioral arm of the study, with the exception that participants will not complete an episodic thinking task, and the MRI screening form may be reviewed with the participant to ensure safety and eligibility.

Eligible participants will be scheduled for an additional session to be completed within the next 30 days. The second session will last approximately an hour and a half to two hours. Participants may be asked to abstain from eating or drinking (except water) for approximately 2 hours prior to their sessions and engaging in any activity that may influence appetite. Participants who are not about 2 hours post prandial or have experienced a major life event that may influence their performance on study measures and tasks may have their appointment rescheduled. As in the first visit, participants will have their blood glucose measured and then offered a PowerBar to consume prior to completing all study related tasks. In this visit, participants will again have blood glucose measured three separate times (e.g. beginning of session, 30 minutes after consuming PowerBar, and at the end of the session).

In the second visit, female participant will again be asked to provide a urine sample to confirm non-pregnancy status. Eligible participants will be randomly assigned to one of two groups, EFT or ERT, and complete an episodic thinking task identical to the thinking task in the first visit of the behavioral study. They may also be asked to complete decision making tasks while engaged in episodic thinking and undergoing an fMRI without contrast scan at their second session. Prior to the scan, MRI safety trained personnel will assess the safety of all participants. During the fMRI scan, the participant will be given a small box with buttons to press in response to the display that appears on the screen above them within the machine. The participant will be selecting objects that they prefer in decision-making tasks. Additionally, interested participants may have the opportunity to receive a copy of their brain images.

Following their last session, all participants will be debriefed.

Pilot participants will complete identical procedures, but may complete fewer sessions and/or activities than those described above.

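### Section 4.1 randomises the fMRI arm to EFT versus ERT, but 17.1 analyses brain function by poverty/neutral as well and 17.2 applies the four-cell interaction sample size to imaging; one imaging design must be stated.

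*Combined protocol and SAP*

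**What the plan says.** Section 4.1 describes the two arms differently. For the behavioral arm, "subjects in the behavioral arm will be randomized to poverty/neutral scenarios crossed with EFT/ERT in a 2 x 2 factorial design". For the imaging arm, "Subjects in the fMRI arm will be randomized to one of two groups: episodic future thinking (EFT) versus episodic recent thinking (ERT) control".

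Section 10.1, under the fMRI arm, gives the same two-group assignment: "Eligible participants will be randomly assigned to one of two groups, EFT or ERT, and complete an episodic thinking task identical". It describes no poverty or neutral scenario for scanned subjects.

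Section 17.1 plans a factorial ANCOVA of delay discounting, executive function and "fMRI-measured brain function for subjects randomly assigned to poverty/neutral conditions and EFT/ERT". Its imaging prediction reads "We also predict when participants who receive EFT under challenge of poverty that EFT will increase activation in brain regions", naming LPFC, AC and hippocampus, and the comparison is "relative to those who receive EFT under similar challenges".

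Section 17.2 derives 17 subjects per group, 68 in total, for the poverty by EFT interaction on discounting, and applies it as "34 per site in the behavioral portion and in the imaging portion". It closes with "To be conservative, we will study up to 100 subjects", without saying whether that number covers one arm or both.

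Section 1.2 states an activation hypothesis for EFT with no poverty condition. Section 2.1 makes activation part of the primary endpoint.

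**The concern.** An analysis can only use a randomised factor that the design supplies. Section 4.1 supplies one factor to the fMRI arm; 17.1 and 17.2 use two. For a component of the primary endpoint, the randomisation, the model and the sample-size basis therefore do not describe the same study.

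The choice determines how scanned subjects are allocated, what they are shown and which contrast is the planned imaging test. If it is left open, it will be settled during conduct or after the data are seen. The power statement for imaging also cannot be relied on until the effect it refers to is known to exist in that arm.

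**Working it through.** **1. The sections side by side.**

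| Section | Factors for imaging | Groups |
|---|---|---|
| 1.2 | EFT; no poverty condition | not stated |
| 4.1 | EFT/ERT | 2 |
| 10.1, fMRI arm | EFT/ERT | 2 |
| 17.1, model | poverty/neutral and EFT/ERT | 4 |
| 17.1, prediction | EFT under poverty | comparator unclear |
| 17.2 | poverty by EFT interaction | 4 (68/17) |

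Section 4.1 carries the contradiction, because it treats the two arms differently in one response. Section 10.1 is consistent with it but adds little: it also assigns the behavioral arm to two groups, EFT or ERT, without mentioning poverty, although 4.1 makes that arm a 2 x 2. Its silence on poverty therefore proves nothing about the scanner.

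The comparator in the 17.1 prediction is printed as EFT, so it sets EFT against EFT. ERT is probably meant. Correcting that word leaves the poverty condition in place.

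**2. The plan's sample size.** Inputs from 17.2: interaction effect size 0.35 (read as Cohen's f), alpha 0.05, power 0.80. For a 1-df interaction in four cells, the noncentrality is f² x N and the denominator df is N - 4.

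- N = 67: 0.35² x 67 = 8.21, power 80.5%. This is the smallest N that reaches 80%.
- Rounded up to equal cells: 17 x 4 = 68, power 81.1%.

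The 68 reproduces from the stated 0.35, and it is a four-cell interaction figure. The 0.35 is taken at face value here; whether it follows from the AUC means in 17.2 is a separate matter.

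**3. What the two-group fMRI arm of 4.1 can estimate.** With no poverty factor there is no poverty main effect and no interaction, whatever N is. The ANCOVA reduces to EFT versus ERT, and 68 subjects form two groups of 34 (68/2).

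**4. Detectable effect for that comparison.** Two-sample t test with n per group: noncentrality d x √(n/2), df 2n - 2, two-sided alpha 0.05, 80% power, one test.

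| n per group | Where n comes from | Detectable d |
|---|---|---|
| 25 | 100 subjects over both arms: 100/2/2 | 0.81 |
| 34 | 68 in imaging: 68/2 | 0.69 |
| 50 | 100 in imaging: 100/2 | 0.57 |

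Which row applies is an assumption. The first agrees with the lower end of the local enrolment in 5.1 (100 subjects, 50 per arm).

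Section 17.1 names three regions and gives no multiplicity rule. If they shared alpha by a Bonferroni split (an assumption; 0.05/3 = 0.0167), the detectable d at 34 per group would be 0.80 instead of 0.69.

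**The case against.** The strongest reply is that 17.1 is loosely drafted: poverty belongs to the behavioral outcomes, and imaging was always EFT versus ERT. That does not fit the text, because the imaging prediction names poverty and 17.2 names the imaging portion.

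A better reply is that every scanned subject receives the poverty scenario. With the comparator read as ERT, the prediction becomes a two-group contrast that the arm in 4.1 could test. This is coherent, but no section says it, and it still conflicts with 17.1's random assignment to poverty/neutral. It belongs among the possible resolutions, and its repair differs from the other two.

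Three stronger readings are tempting, and the documents support none of them:

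- **That 68 is too few for imaging.** No activation effect size is given. Going from four cells to two groups does not itself change N for a given 1-df effect size: with f = 0.35 (d = 0.70) the two-group F test also needs N = 67.
- **That the activation hypothesis cannot be tested.** Section 1.2 states it without poverty, 17.1 names an ANCOVA and three regions, and that ANCOVA reduces to EFT versus ERT. What is missing is an unconditional prediction in 17.1 and a sample-size basis in 17.2.
- **That 10.1 shows there is no poverty scenario in the scanner.** It omits poverty for the behavioral arm too.

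It is also fair to say that randomisation to EFT or ERT remains valid and that the repair may be wording only. That limits the cost; it does not remove the contradiction.

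**Conclusion.** The contradiction between 4.1 and section 17 is explicit, and nothing elsewhere resolves it. If 4.1 stands, the poverty and interaction terms in 17.1 are not estimable for imaging, and the 80% power at 68 refers to an effect that is absent from that arm. If 17.1 stands, the randomisation in 4.1 does not supply a factor that the analysis needs. Because activation is part of the primary endpoint, this should be corrected before the plan is relied on.

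Confidence is high for the contradiction. The numerical part is conditional: detectable d runs from 0.57 to 0.81 for one test, depending on what the limit of 100 covers, and is larger if the three regions share alpha. Whether the imaging sample is adequate cannot be judged until an activation effect size or an acceptable detectable effect is stated.

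**What to change.** State one imaging design and reconcile 4.1, 10.1, 17.1 and 17.2 with it. The documents do not show which is intended, so the sponsor must choose.

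1. **No poverty scenario in the scanner.** In 17.1, limit the factorial ANCOVA to the behavioral arm and add, for example: *In the fMRI arm, activation in LPFC, AC and hippocampus will be compared between EFT and ERT and is predicted to be higher with EFT.* In 17.2, delete the reference to the imaging portion and give the imaging N with its two-group detectable effect (for example d = 0.69 at 34 per group, 80% power, two-sided 0.05, single test) or a sourced activation effect size. Say how the three regions share alpha. Cost: wording in 17.1 and 17.2, with no added subjects or procedures.
2. **Every scanned subject receives the poverty scenario.** Describe it in 4.1 and 10.1, drop random assignment to poverty/neutral for imaging in 17.1, correct the comparator to ERT, and give the same two-group sample-size basis. Cost: wording in four sections, with no added randomised factor.
3. **Poverty/neutral is randomised in the scanner.** Say so in 4.1 and 10.1, correct the comparator in 17.1, and give an imaging effect size in 17.2. Cost: the fMRI arm as described in 4.1 gains a randomised factor, and its sample size must be justified for the imaging interaction.

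In every case, 17.2 should say whether the limit of 100 is per arm or overall.

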10.0 Procedures Involved

10.1 *Provide a description of **all research procedures or activities** being performed and when they are performed once a subject is screened and determined to be eligible. Provide as much detail as possible.*

NOTE: This should serve as a blueprint for your study and include enough detail so that another investigator could pick up your protocol and replicate the research. For studies that have multiple or complex visits or procedures, consider the addition of a schedule of events table in in your response.

Response:

Behavioral Arm: Upon arrival to the Division of Behavioral Medicine (G56 Farber Hall), participants will be greeted and escorted to a private interview room where they will be given a verbal explanation about the study and provide documented consent. Two copies of the consent form will be signed by all parties involved, person obtaining consent and the participant. One copy will be obtained by study personnel and one copy will be given to participants for their records. After signing the consent forms, participants will have their blood glucose measured. Participants will then consume a PowerBar and begin completing study related tasks in which they will have their HbA1c, blood pressure, height and weight measured to calculate BMI, and complete measures of delay discounting and study questionnaires including demographics, consumption, alcohol, tobacco substance use, time perspective, and prospective memory. Measures and questionnaires may be completed on either the computer or paper/pencil labelled only with the participant's ID number. About 30-45 minutes after consuming the PowerBar participants will have their blood glucose measured again. In addition, participants will sign forms for release of their relevant medical records to confirm their eligibility (e.g., diagnosis with prediabetes, hypertension and/or hyperlipidemia, MRI

eligibility). Participants will be given a choice as to whether they would like their screening results shared with them and/or with their physician. If participants have values at a certain critical level (e.g. critically high blood pressure) they may be automatically notified. Participants may also complete a urine drug screen to confirm non-substance abuse and female participants may complete a urine pregnancy test to ensure eligibility.

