After completing all study tasks, questionnaires, measures etc. for the first session, participants may have their blood glucose measured again. Blood glucose will be measured up to 3 separate times during this visit. The first visit is expected to last between two to two and a half hours.

If eligible, participants will be scheduled for an additional session to be completed within the next four weeks. The second session will last approximately two to two and a half hours. Participants may be asked to abstain from eating or drinking (except water) for approximately 2 hours prior to both of their sessions and engaging in any activity that may influence appetite. Participants who are not about 2 hours post prandial or have experienced a major life event that may influence their performance on study measures and tasks may have their appointment rescheduled. As in the first visit, participants will have their blood glucose measured and then offered a PowerBar to consume prior to completing all study related tasks. In this visit, participants will again have blood glucose measured three separate times (e.g. beginning of session, about 30-45 minutes after consuming PowerBar, and at the end of the session).

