Participants will be randomly assigned to one of two groups, EFT or ERT, and complete an episodic thinking task. Participants will be randomized by stratifying for education level and sex. The episodic thinking task to generate episodic cues will be similar to the tasks used in our previous studies on EFT's effect (Daniel et al., 2013). Each group will list and describe events for different time periods. The episodic component of the thinking task will occur while the participants are asked to describe what they are imagining about each event (e.g., vacations, weddings, parties, and so forth). EFT participants will list positive future events they are looking forward to and list events that could happen at different general future time points (e.g., 1 month, 2-6 months, 7-12 months). In contrast, the ERT group will list positive recent events (events that have already happened) that they have enjoyed that have occurred at different general time points (e.g., a few hours ago, 1 day ago, 2-6 days ago, 7-12 days ago). All participants will rate the salience, valence, arousal, feasibility and vividness of each event and events with the highest ratings for vividness will be used in the generation of episodic cues. An "imagery" score may be calculated by averaging the frequency/vividness scores for each event. Reductions in rate of discounting occur at higher levels of episodic imagery (Peters & Buchel, 2010). Additionally, participants will record their highest rated events into audio cues.

Participants may also be instructed to use and think about their episodic cues as they engage in a set of executive function tasks (e.g., The Virtual Week) and other decision making tasks such as measures of delay discounting (e.g., discounting of money, food, sedentary behaviors/physical activity, future health; a series of single and cross commodity discounting tasks) and food preferences. Participants will be randomized to which cues (future or recent) they will be instructed to think about when engaging in The Virtual Week task. Executive function tasks may take place on a computer screen or paper and pencil. Participants will complete questionnaires regarding their attention to their episodic cues while engaged in study tasks.

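### Covariates enter the ANCOVA only after a significant group difference, so session-1 discounting and the stratification factors would usually be left out; pre-specifying them for discounting outcomes is a cheap, conditional gain in power

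*Combined protocol and SAP*

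**What the plan says.** Section 17.1 plans a factorial ANCOVA for discounting, executive function and brain activation. It names no covariate, and its only rule on adjustment is "Covariates will be used if significant differences between groups are observed in subject characteristics". It gives no test level and no list of candidate characteristics.

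Section 10.1 supplies the obvious candidates. At the first visit participants "complete measures of delay discounting and study questionnaires including demographics". On allocation it says "Participants will be randomized by stratifying for education level and sex"; the number of education levels is not given, and no stratification is stated in the fMRI-arm text. Section 4.1 describes a 2 x 2 design for the behavioral arm, while "Subjects in the fMRI arm will be randomized to one of two groups".

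The timing of assignment differs by arm:

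- **fMRI arm.** The account of the second visit says "Eligible participants will be randomly assigned to one of two groups, EFT or ERT".
- **Behavioral arm.** The first visit ends with "If eligible, participants will be scheduled for an additional session to be completed within the next four weeks", and random assignment is described after that, which reads as session 2. But the fMRI arm's first visit is said to match the behavioral one "with the exception that participants will not complete an episodic thinking task", and its later thinking task is called "identical to the thinking task in the first visit of the behavioral study". Both remarks imply a thinking task at the behavioral arm's first visit.

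**The concern.** Adjustment is useful because a covariate explains outcome variance. A significance test between randomised groups does not measure that; it detects chance imbalance. A strong predictor that happens to be balanced is left out, and an irrelevant variable that happens to be imbalanced is put in. The variable most likely to predict session-2 discounting is session-1 discounting, and the rule would usually discard it. The rule also tends to drop the stratification factors, because stratification makes them balanced.

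At stake is power in a small trial: 68 subjects by the stated calculation, with up to 100 planned. Leaving the test level and candidate list open also gives the analyst a choice that could be closed in advance.

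**Working it through.** **Inputs.** Section 17.2 gives SD 0.28, alpha 0.05, AUC cell means of 0.54 (ERT/neutral), 0.36 (ERT/poverty), 0.63 (EFT/neutral) and 0.54 (EFT/poverty), and N=68 or up to 100. Assumed here: two-sided tests, a 5% level for the covariate screen, and correlations r between session-1 discounting and the outcome of 0.3, 0.5 and 0.7.

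**The plan's own figure.** A 1-df F test with four cells and effect size f=0.35 has power 81.1% at N=68, so the stated 17 per group reproduces. However, 0.35 is the overall f across the four cell means (0.3503). The contrasts are:

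- Interaction: (0.54 - 0.36) - (0.63 - 0.54) = 0.09, so f = 0.09/(4 x 0.28) = 0.080.
- Poverty main effect: (0.54 + 0.63)/2 - (0.36 + 0.54)/2 = 0.585 - 0.45 = 0.135, so f = 0.135/(2 x 0.28) = 0.241.

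**How often the rule admits a covariate.** For an unstratified characteristic, one four-cell test admits it in 5% of trials. Three separate factorial contrasts admit it in about 1 - 0.95^3 = 14%. Simulation (8,000 trials per scenario) gave 4.7-5.4% and 13.9-14.2%. So it is left out in about 86-95% of trials, whatever its prognostic value. With EFT/ERT stratified in assumed blocks of 2, sex was significant on that contrast in 0 of 32,000 trials.

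**Power for the poverty main effect.** Noncentral t with k=4 cells and c covariate terms in total:

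- SE = 2 x 0.28/sqrt(N) x sqrt[(1 - r^2)(1 + c/(N - k - c - 1))], with df = N - k - c. The last factor allows for chance imbalance.
- Unadjusted, N=68: SE = 0.56/8.246 = 0.0679; noncentrality 0.135/0.0679 = 1.988; df 64; power 49.9%.
- Session-1 discounting only, r=0.5, N=68: variance factor 0.75 x (1 + 1/62) = 0.762; noncentrality 1.988/sqrt(0.762) = 2.277; df 63; power 61.1%.

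| N | Terms c | r=0 | r=0.3 | r=0.5 | r=0.7 | Break-even r |
|---|---|---|---|---|---|---|
| 68 (unadjusted 49.9%) | 1 | 49.3% | 53.0% | 61.1% | 77.6% | 0.128 |
| 68 | 4 | 47.3% | 51.0% | 58.9% | 75.5% | 0.256 |
| 68 | 6 | 46.0% | 49.6% | 57.4% | 74.0% | 0.313 |
| 100 (unadjusted 66.5%) | 1 | 66.0% | 70.1% | 78.3% | 91.4% | 0.104 |
| 100 | 4 | 64.6% | 68.7% | 76.9% | 90.5% | 0.207 |
| 100 | 6 | 63.6% | 67.7% | 76.0% | 89.8% | 0.254 |

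The rows with 4 and 6 terms treat every term as open to chance imbalance and give the extra terms no prognostic value. If stratification balances the extra terms, break-even falls back to about 0.13-0.14 at N=68 and 0.11 at N=100.

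**Power under the rule as written.** Simulated at N=68 for r from 0.3 to 0.7, it was 49.5-51.0% with one F test and 49.7-53.4% with three contrasts, close to unadjusted.

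**Validity.** Simulated Type I error (12,000 trials, N=68) was 3.9-5.2% under the rule and 4.9-5.3% with pre-specified covariates.

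**Interaction.** N=68: noncentrality 0.09/(4 x 0.28/sqrt(68)) = 0.663, power 10.0%. With session-1 discounting at r=0.7 it is 14.8%.

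**The case against.** **The gain is conditional.** The documents give no correlation. At r=0.3 and six terms, power is 49.6% against 49.9% unadjusted, a slight loss. The large gains need r of 0.5 or more. This stands, and is why the benefit is given as a range.

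**No single break-even applies.** A reader might take 0.26 as the threshold. It holds only for four terms all open to chance imbalance, for example sex, two-level education and site besides session-1 discounting, or sex and three-level education without site. The documents do not give the number of education levels or say whether stratification covers the poverty factor. The supportable range at N=68 is 0.13 to 0.31.

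**The power figures sit where timing is unresolved.** The poverty contrast belongs to the behavioral arm, where session-1 discounting may or may not precede assignment. This stands. A reader might infer that it is a post-assignment measure there, but section 10.1 points both ways. In the fMRI arm it precedes assignment as written.

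**Stronger readings the documents do not support.** The rule does not invalidate the tests, since simulated Type I error is not inflated. Adjustment does not rescue the interaction on which the study was sized. No gain is shown for brain activation or executive function. Nor can one say that site is ignored: section 10.3 refers to a section 6.6.3 that is not in these documents and may deal with it.

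**Conclusion.** The point holds as a matter of efficiency. The rule in section 17.1 selects covariates on chance imbalance and would usually omit both a plausible predictor of discounting and the factors used in randomisation. For the poverty main effect, pre-specifying session-1 discounting would raise power from 50% to 53-78% at N=68 and from 67% to 70-91% at N=100, over assumed r of 0.3 to 0.7.

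Break-even at N=68 is 0.13 for session-1 discounting alone, or if stratification balances the other terms, rising to 0.31 with six terms open to imbalance (0.10 to 0.25 at N=100). If nothing is prognostic, the loss at N=68 is up to about 3 points with four terms and about 4 with six.

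The conclusion rests on the section 17.2 means and SD, on an assumed 5% screen, and on session-1 discounting being measured before assignment. It is limited to discounting outcomes. The change is worth making, but the trial's validity does not depend on it.

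**What to change.** Replace the covariate sentence in section 17.1 with: *Discounting outcomes will be adjusted for the session-1 value of the same task (otherwise session-1 monetary discounting) where it was measured before assignment and cueing, and for the factors used to stratify randomisation in that arm, regardless of observed baseline differences.*

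Alongside it:

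- Reconcile section 10.1 on which visit holds the behavioral arm's assignment and thinking task. Use session-1 discounting in that arm only if it precedes assignment.
- State how many education levels are used, whether the fMRI arm is stratified, and which discounting tasks are given at session 1. The documents do not show that every session-2 task has a session-1 counterpart.
- Treat site as optional, and check it against the missing section 6.6.3 first.

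The cost is one sentence and a clarification, using measures already planned, plus the possible loss of power stated in the verdict.
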